6.26.2. Subjects with Elevations in Liver Transaminases or Bilirubin at Baseline

Drug-induced liver injury monitoring in subjects with elevations in liver transaminases or bilirubin at baseline should be performed throughout the study according to the procedures summarized below.

- If subjects with abnormal baseline liver indices develop elevations of ALT $>3 \times$ baseline or ≥ 300 U/L (whichever occurs first) during the study, repeat testing should be performed within 2 - 5 days.

- If there are persistent elevations (ALT $>3 \times$ baseline, or ≥ 300 U/L) upon repeat testing, then close observation (testing and physical examination 2 to 3 times per week) should be implemented and discontinuation of study drug should be considered.
- Discontinue the study drug if any of the following occur:
 - ALT increases to $>5 \times$ baseline measurements or ≥ 400 U/L (whichever occurs first).
 - ALT increase $>3 \times$ baseline measurements or ≥ 300 U/L (whichever occurs first) AND the increase is accompanied by a concomitant increase in TBL to $> 2 \times$ ULN.
 - ALT increase $>3 \times$ baseline measurements or ≥ 300 U/L (whichever occurs first) with the appearance of fatigue, nausea, vomiting, right upper quadrant pain or tenderness, fever, rash, and/or eosinophilia ($> 5\%$)

For any subjects who present with a constellation of syndromes indicative of liver disease as per the Investigator's overall assessment (i.e., fatigue, nausea, vomiting, right upper quadrant pain or tenderness, fever, rash, and/or eosinophilia [$> 5\%$]), perform liver function tests to determine if liver disease is worsening.

Re-initiation of investigational medicinal product may be considered after consultation with the CRO Medical Monitor and DMC assessment.

6.26.3. Close Observation for Suspected Drug-Induced Liver Injury

For all subjects, close observation for suspected drug-induced liver injury includes the following within 72 hours of suspected drug-induced liver injury:

- Repeating liver enzyme (ALT, AST, and alkaline phosphatase) and serum bilirubin tests 2 or 3 times weekly.
- The frequency of repeat testing can decrease to once a week or less if abnormalities stabilize or the study drug has been discontinued and the subject is asymptomatic.
- Obtaining a more detailed history of symptoms and prior or concurrent diseases.
- Obtaining a history of concomitant drug use (including nonprescription medications and herbal and dietary supplement preparations), alcohol use, recreational drug use, and special diets.
- Ruling out acute viral hepatitis types A, B, C, D, and E; autoimmune or alcoholic hepatitis; hypoxic/ischemic hepatopathy; and biliary tract disease.
- Obtaining a history of exposure to environmental chemical agents.
- Obtaining additional tests to evaluate liver function, as appropriate (e.g., INR, direct bilirubin).
- Considering gastroenterology or hepatology consultations.
- Subjects who live far from study sites can be evaluated locally for history, physical exam, and laboratories, provided results can be communicated promptly to the site Investigator.

6.27. Removal of Subjects from the Study

The Investigator may withdraw a subject from the study for any of the following reasons:

- Withdrawal of consent
- Non-compliance as determined by the Investigator or Sponsor
- At the discretion of the Investigator and/or study Medical Monitor and/or the DMC if it is in the best interest of the subject
- Lost to follow-up

At any time, the Investigator can remove a subject from study treatment and/or the study if deemed necessary for subject safety. The Sponsor also reserves the right to terminate the study at any time. All data normally collected at completion of the study must be collected at the time of the subject's early termination or termination of the study.

The Investigator will discuss with the subject or legally acceptable representative(s) the most appropriate way to withdraw to ensure the subject's health. Should a subject (or a legally acceptable representative) request or decide to withdraw consent, all efforts will be made to complete and report the observations as thoroughly as possible up to the date of withdrawal.

7. PLANNED STATISTICAL METHODS

7.1. Endpoints

Details will be provided in the statistical analysis plan (SAP).

7.1.1. Efficacy Endpoints

7.1.1.1. Primary Endpoint

The primary endpoint is:

- Proportion of subjects who achieve improvement in liver fibrosis, defined as \geq one stage (NASH CRN fibrosis score) and no worsening of steatohepatitis (defined as no increase in NAS for ballooning, inflammation, or steatosis) at Week 24.

7.1.1.2. Secondary Endpoints

The secondary endpoints are:

- Proportion of subjects who achieve resolution of steatohepatitis (defined as a NAS of 0-1 for inflammation, 0 for ballooning, and any value for steatosis) and no worsening of liver fibrosis as determined by the NASH CRN criteria at Week 24 and Week 96.
- Proportion of subjects who achieve improvement in liver fibrosis, defined as \geq one stage (NASH CRN fibrosis score) and no worsening of steatohepatitis (defined as no increase in NAS for ballooning, inflammation, or steatosis) at Week 96.
- Proportion of subjects who achieve improvement in liver fibrosis, defined as \geq one stage (NASH CRN fibrosis score) at Week 24 and Week 96.
- Change from baseline in hepatic fat fraction measured by MRI-PDFF at Week 24 and Week 96.
- Change from baseline of lipoproteins – triglycerides, Non-HDL-C, HDL-C and LDL-C.
- Change from baseline of markers of glycemic control – HbA1c, C-peptide, Adiponectin and HOMA-IR.
- Change from baseline in non-invasive markers of fibrosis – ELF, Pro-C3, C3M, NIS-4 and liver stiffness assessed by transient elastography (FibroScan®).
- Change from baseline of body weight.

7.1.1.3. Exploratory Efficacy Endpoints

The exploratory endpoints are:

7.1.2. Safety Endpoints

The safety endpoint is safety and tolerability of EFX in subjects with NASH.

Safety analyses include: summaries of extent of exposure, AEs, clinical laboratory tests, endogenous FGF21, ECG, BMD, vital sign assessments, body weight, anti-drug antibody (ADA) and neutralizing antibody (NAB) assessments, and concomitant medication usage.

7.2. Analysis Conventions

All individual subject data will be listed as measured. All statistical summaries and analyses will be performed using Statistical Analysis System (SAS[®]) software (SAS Institute, Cary, North Carolina, USA).

7.3. Analysis Sets

The study analysis sets are detailed below.

7.3.1. Full Analysis Set (FAS)

The primary analysis set for non-histological efficacy analyses will be the Full Analysis Set (FAS) which will include all subjects who were randomized into the study.

Subjects who receive a dose of study drug other than that to which they were randomized for the entire duration of treatment will be analyzed according to treatment group to which they were randomized.

7.3.2. Per Protocol (PP) Sets

The Per Protocol (PP) Sets will be a subset of the FAS and will include subjects who finish scheduled visits with applicable assessments and do not have major protocol deviations.

7.3.3. Safety Set

All subjects who receive at least one dose of study drug will be included in the Safety Set. All safety endpoints will be summarized using the Safety Set and will be based on actual treatment received if this differs from the randomized treatment.

7.3.3.1. Pharmacokinetics Set

The PK analysis set will include all randomized subjects who took at least one dose of study drug and for whom concentration data of EFX is available.

7.3.3.2. Biomarkers Analysis Set

The Biomarker Analysis Set will include data from subjects in the Safety Analysis Set who have the necessary baseline and on-study measurements to provide interpretable results for the specific parameters of interest.

7.3.3.3. Liver Biopsy Analysis Set (LBAS)

The primary analysis set for histological efficacy analyses will be the Liver Biopsy Analysis Set (LBAS), which will be a subset of the FAS. It will include all FAS subjects who have the baseline and on-study liver biopsy results.

7.3.3.4. MRI-PDFF Analysis Set

The MRI-PDFF Analysis Set will be a subset of the FAS. It will include all FAS subjects who have baseline and on-study measurements assessed by MRI-PDFF.

7.4. Data Handling Conventions

Missing data can have an impact on the interpretation of the trial data. In general, values for missing data will not be imputed unless specified.

Where appropriate, safety data for subjects that did not complete the study will be included in summary statistics. For example, if a subject received study drug, the subject will be included in a summary of AEs according to the treatment received; otherwise, if the subject is not dosed then they will be excluded from the summary. If safety laboratory results for a subject are missing for any reason at a time point, the subject will be excluded from the calculation of summary statistics for that time point. If the subject is missing a baseline value, then the subject will be excluded from the calculation of summary statistics for the baseline value and the change from baseline values.

Values for missing safety laboratory data will not be imputed; however, a missing baseline result will be replaced with a screening result, if available. If no pre-treatment laboratory value is available, the baseline value will be assumed to be normal (i.e., no grade [Grade 0]) for the summary of graded laboratory abnormalities.

Values for missing vital signs data will not be imputed; however, a missing baseline result will be replaced with a screening result, if available.

Further details of data handling conventions and transformation will be provided in the SAP.

7.5. Estimands

In line with ICH E9 (R1) addendum, 5 attributes (treatment, population, endpoint, intercurrent events, and population-level summary) have been specified to translate the primary and key secondary efficacy objectives into treatment effects that are to be estimated (estimands).

The treatment conditions of interest are EFX 28 mg administered weekly, and EFX 50 mg administered weekly, and are compared with matching placebo administered weekly.

The treatment effect is assessed by the primary histological endpoint of improvement in liver fibrosis and no worsening of steatohepatitis.

The population of subjects targeted is adults with NASH with liver fibrosis as defined by the inclusion/exclusion criteria.

Intercurrent events are handled through a composite strategy (see Table 6).

The population-level summary of the treatment effect will be quantified by comparing observed responder proportions supported by the risk ratio of investigational product compared to placebo (EFX 28 mg versus placebo or EFX 50 mg versus placebo) calculated from the odds ratio obtained through Cochran-Mantel-Haenszel (CMH) test detailed in the Statistical Analysis Plan.

Table 6. Approach for Intercurrent Events for the Primary Endpoint

Intercurrent Event	Status
Start of additional therapy with potential to impact NASH condition (i.e. rescue medication)	Subject defined as a non-responder (even if a post-treatment biopsy is available)
MELD score ≥ 15	Subject defined as a non-responder (even if a post-treatment biopsy is available)
Hepatic decompensation event	
Unscheduled biopsy showing progression to F4	Subject will be counted as a non-responder
Bariatric surgery	Subject defined as a non-responder

The estimands attributes for all secondary histological endpoints are defined in the same manner as for the primary endpoint described above.

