4.2. Inclusion Criteria

Subjects must meet all the following inclusion criteria to be eligible for study participation:

1. Males and non-pregnant, non-lactating females between 18 - 75 years of age inclusive, at the time of the screening visit.
2. Previous history or presence of 2 out of 4 components of metabolic syndrome (obesity, dyslipidemia, elevated blood pressure, elevated fasting glucose) or type 2 diabetes.
3. **Initial Screening Visit:** After a signed informed consent and confirmation of clinical risk profile associated with NASH, a screening lab panel and elastography will be measured for all subjects during an initial screening period:

- a. FibroScan® median liver stiffness > █

- b. CAP █

Note: All subjects must complete a FibroScan® examination during the screening period. However, the median liver stiffness and CAP inclusion criterion do not apply to subjects with an eligible historical liver biopsy performed \leq 180 days prior to randomization which confirmed fibrosis 1-3 and a NAS \geq 4.

If a historical value for FibroScan® is available in the past 3 months prior to the Screening Visit, then the FibroScan® does not need to be repeated.

- c. AST $>$ 17 for females and $>$ 20 for males;

Note: The AST inclusion criterion does not apply to subjects with an eligible historical liver biopsy performed \leq 180 days prior to randomization which confirmed fibrosis 2-3 and a NAS \geq 4.

- d. Estimated glomerular filtration rate (eGFR) \geq 60 mL/min, as calculated by the CKD-EPI equation;
- e. HbA1c \leq 9.5% (or serum fructosamine \leq 381 μ mol if HbA1c is unavailable);
- f. INR \leq 1.3, unless due to therapeutic anticoagulation;
- g. Direct bilirubin \leq ULN;
- h. Total bilirubin \leq upper limit of normal (ULN), unless due to an alternate etiology such as Gilbert's syndrome or hemolytic anemia;
- i. Creatinine kinase $<$ 3 x ULN;
- j. Platelet count \geq 140,000/ μ L;
- k. Triglyceride level \leq 500 mg/dL;
- l. ALT $<$ 5 x ULN;

- m. AST < 5 x ULN;
- n. ALP < 2 x ULN.

Note: Subjects meeting all of the above components will move into the next screening phase.

4. Documented historical stability (4 weeks to 6 months prior to screening) of ALT and AST levels showing no worsening at screening based on the following:
 - a. If the historical and screening ALT and AST values are both $\leq 1.5 \times$ the upper limit of normal (ULN), there is no limit to the difference between the values.

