6.25.1. Hepatic Events Adjudication Committee

A key objective of this study is to prevent progression to cirrhosis and associated complications. Clinical events that constitute the clinical outcomes endpoint include:

- 1) Progression to cirrhosis as defined by a liver biopsy showing F4 fibrosis according to the NASH CRN classification, as assessed by the central reader.
- 2) Events of hepatic decompensation including:

- a) Clinically apparent ascites requiring treatment
- b) HE of Grade 2 or above (according to the West Haven criteria defined in [Appendix E](#)) requiring treatment
- c) Portal hypertension-related upper gastrointestinal bleeding identified by endoscopy and requiring hospitalization, including events of bleeding from esophageal varices, gastric varices, and portal hypertensive gastropathy
- 3) Liver transplantation or qualification for liver transplantation, defined as MELD score ≥ 15 (unless due to therapeutic anticoagulation) on at least 2 consecutive occasions at least 4 weeks apart
- 4) All-cause mortality

Each of the clinical events (except histologic progression to cirrhosis, all-cause mortality and liver transplantation) will require confirmation by a Hepatic Events Adjudication Committee. All deaths will be reviewed by this committee to determine if they are liver-related.

If there is clinical evidence that a subject has progressed to cirrhosis (e.g., based on the presence of new esophageal varices, changes in biomarkers [including, but not limited to, low serum albumin, high serum bilirubin, a low platelet count, prolonged INR, or elevated liver stiffness], or development of other clinical signs or symptoms of cirrhosis), the subject should undergo repeat liver biopsy for confirmation of progression to cirrhosis (F4 fibrosis as assessed by the central reader according to the NASH CRN classification) at the discretion of the principal investigator (PI).

Once the clinical event (except histological progression to cirrhosis, all-cause mortality and liver transplantation) is confirmed by the Hepatic Events Adjudication Committee, the subject will discontinue from the study. Subjects who experience histological progression to cirrhosis, all-cause mortality and liver transplantation will be discontinued from the study, but do not require confirmation from the adjudication committee prior to discontinuation.

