GGT	GGT increased	>ULN - 2.5 x ULN if baseline was normal; >2 - 2.5 x baseline if baseline was abnormal	>2.5 - 5.0 x ULN if baseline was normal; >2.5 - 5.0 x baseline if baseline was abnormal	>5.0 - 20.0 x ULN if baseline was normal; >5.0 - 20.0 x baseline if baseline was abnormal	>20.0 x ULN if baseline was normal; >20.0 x baseline if baseline was abnormal

Hematology	CTCAE Term	Grade 1	Grade 2	Grade 3	Grade 4
Hemoglobin	Anemia	<LLN - 10.0 g/dL; <LLN - 6.2 mmol/L; <LLN - 100 g/L	<10.0-8.0 g/dL; <6.2 - 4.9 mmol/L; <100 - 80g/L	<8.0 g/dL; <4.9 mmol/L; <80 g/L	
Hemoglobin	Hemoglobin increased	>ULN & increase in >0 - 2 g/dL	>ULN & increase in >2 - 4 g/dL	>ULN & increase in >4 g/dL	
CD4 lymphocytes	CD4 lymphocytes decreased	<LLN - 500/mm ³ ; <LLN - 0.5 x 10e9/L	<500 - 200/mm ³ ; <0.5 - 0.2 x 10e9/L	<200 - 50/mm ³ ; <0.2 - 0.05 x 10e9/L	<50/mm ³ ; <0.05 x 10e9/L
Neutrophils	Neutrophil count decreased	<LLN - 1500/mm ³ ; <LLN - 1.5 x 10e9 /L	<1500 - 1000/mm ³ ; <1.5 - 1.0 x 10e9 /L	<1000 - 500/mm ³ ; <1.0 - 0.5 x 10e9 /L	<500/mm ³ ; <0.5 x 10e9 /L
White Blood Cell (WBC) Count	White blood cell decreased	<LLN - 3000/mm ³ ; <LLN - 3.0 x 10e9 /L	<3000 - 2000/mm ³ ; <3.0 - 2.0 x 10e9 /L	<2000 - 1000/mm ³ ; <2.0 - 1.0 x 10e9 /L	<1000/mm ³ ; <1.0 x 10e9 /L
Platelet Count	Platelet count decreased	<LLN - 75000/mm ³ ; <LLN - 75.0 x 10e9 /L	<75000 - 50000/mm ³ ; <75.0 - 50.0 x 10e9 /L	<50000 - 25000/mm ³ ; <50.0 - 25.0 x 10e9 /L	<25000/mm ³ ; <25.0 x 10e9/L

Coagulation	CTCAE Term	Grade 1	Grade 2	Grade 3	Grade 4
INR	INR increased	>1.2 - 1.5; >1 - 1.5 x baseline if on anticoagulation	>1.5 - 2.5; >1.5 - 2.5 x baseline if on anticoagulation	>2.5; >2.5 x baseline if on anticoagulation	

For other parameters, not listed in [Table 6](#) separate laboratory shift tables will present directional shifts from baseline to above the laboratory standard upper limit

CONFIDENTIAL

Statistical Analysis Plan

Sponsor Name: Akero Therapeutics, Inc.
Sponsor Protocol ID: AK-US-001-0102

of normal (ULN) or below the lower limit of normal (LLN) using the maximum increase and/or decrease observed throughout the course of treatment and including the 30-day follow-up visit. Scheduled and unscheduled assessments will be included in this analysis.

Evaluation of drug-induced serious hepatotoxicity (eDISH) plot will be provided to display peak serum ALT and total bilirubin (TB) levels for each subject. The peak serum AST versus TB levels for each subject will also be provided.

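### Protocol Table 6 counts any MELD score of 15 or more as non-response, without the anticoagulation exemption that section 6.25.1 applies to the same threshold

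*Protocol*

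**What the plan says.** Protocol 7.5 adopts a composite strategy for intercurrent events. One row of Table 6 is "MELD score ≥ 15", and its status entry is "Subject defined as a non-responder (even if a post-treatment biopsy is available"). The row names no cause, asks for no repeat value and makes no reference to baseline. The same section extends these attributes to every secondary histological endpoint. SAP 3.4 extends them to the exploratory ones as well.

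Protocol 6.25.1 uses the same threshold to define qualification for liver transplantation as a clinical outcome event. There it counts "unless due to therapeutic anticoagulation) on at least 2 consecutive occasions at least 4 weeks apart". Events of this kind "will require confirmation by a Hepatic Events Adjudication Committee".

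Protocol 4.2, criterion 3f, caps INR at 1.3 at screening "unless due to therapeutic anticoagulation", so subjects with an anticoagulant-raised INR are eligible. The SAP allows for anticoagulation when it grades INR abnormalities: Table 6 in SAP 7.7.3 rescales the grade limits, for example to "1.5 x baseline if on anticoagulation".

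SAP 3.4 refers intercurrent events to its own Table 1. Only the title of that table can be read in the released text.

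**The concern.** INR is a component of MELD, so an anticoagulant can raise the score without any change in liver function. Section 6.25.1 and criterion 3f both recognise this. The Table 6 row does not, and it overrides the biopsy.

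The two rules also interact. A subject whose MELD rise meets 6.25.1 and is confirmed by the committee leaves the study. A subject whose MELD rise is due to anticoagulation is exempt there, stays in, can have the Week 24 biopsy and enters the Liver Biopsy Analysis Set. On the literal wording of Table 6 that subject is then scored a failure whatever the biopsy shows. A subject already at 15 or more on Day 1 because of anticoagulation could be a non-responder from the first post-baseline value.

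At stake is whether responder status means what the estimand says it means for these subjects. If the gap stays open, its interpretation could also be settled after responder status is known.

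**Working it through.** **1. The provisions side by side**

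| | Protocol 7.5, Table 6 | Protocol 6.25.1 |
|---|---|---|
| Threshold | MELD 15 or more | MELD 15 or more |
| Anticoagulation exemption | none stated | yes |
| Repeat value | none stated | two consecutive, at least 4 weeks apart |
| Committee confirmation | none stated | yes |
| Consequence | non-responder despite biopsy | clinical outcome event, leaves study |

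No visible text says that the Table 6 row is to be read with the 6.25.1 qualifiers. Criterion 3f puts the exempted subjects into the trial. Anticoagulants are not among the examples in the prohibited or conditionally allowed tables of Protocol 5.3, so they might also be started on study.

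**2. Opportunities to trigger the rule.** Chemistry and coagulation are drawn at Weeks 1, 4, 8, 12, 16, 20 and 24 (Protocol Appendix A; SAP 6.1). That is seven post-baseline visits. On the literal wording one value is enough.

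**3. INR needed to reach MELD 15.** Neither document gives a formula. Assume the conventional one, with each input floored at 1.0:

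MELD = 3.78 ln(bilirubin) + 11.2 ln(INR) + 9.57 ln(creatinine) + 6.43

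With bilirubin and creatinine at the floor, MELD = 6.43 + 11.2 ln(INR). Setting this to 15 gives ln(INR) = 8.57 / 11.2 = 0.765, so INR = 2.15 (2.06 if the score is rounded to a whole number).

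| INR | 1.3 | 1.5 | 2.0 | 2.2 | 2.5 | 3.0 |
|---|---|---|---|---|---|---|
| MELD | 9.4 | 11.0 | 14.2 | 15.3 | 16.7 | 18.7 |

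With bilirubin and creatinine both at 1.2 mg/dL, the constant becomes 6.43 + 0.69 + 1.74 = 8.86, and the threshold INR falls to exp(6.14 / 11.2) = 1.73 (1.65 if rounded). The entry limit on eGFR (60 mL/min or more) restricts how far the creatinine term can go.

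**4. Expected effect on the comparison.** The planned rates, completers and power are redacted, so there is no stated figure to reproduce. Inputs:
- 40 per arm (Protocol 5.2.2) and two-sided alpha 0.05 (SAP 7.6.1).
- EFX response of 46.2% or 61.5%, the Phase 2a results for 28 mg and 50 mg (Protocol 1.4.1.3).
- Placebo response of 10% to 25% (assumed).
- A share f of each arm reclassified (assumed), equally likely as other subjects to be histological responders. Each rate p then becomes p(1 − f).

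Power = Φ{ [Δ√n − 1.96√(2p̄(1−p̄))] / √(p₁(1−p₁) + p₂(1−p₂)) }, an unstratified approximation to the planned CMH test.

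For placebo 15% and EFX 46.2%:

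| f | 0 | 2.5% (1 of 40) | 5% | 10% |
|---|---|---|---|---|
| Difference (points) | 31.2 | 30.4 | 29.6 | 28.1 |
| Power | 87.2% | 85.9% | 84.5% | 81.5% |

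Over placebo 10% to 25% with EFX 46.2%, the loss is 0.7 to 1.7 points at f = 2.5% and 3.1 to 6.9 points at f = 10%. With EFX 61.5% it is at most 1.2 and 5.6 points.

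**The case against.** Four objections have force.

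First, the SAP is dated 07 Feb 2024 and cites Protocol Amendment 4 as its source, so its Table 1 is probably the operational rule. The body of that table is not visible and may already carry the qualifiers. This stands: the gap is shown for the Protocol only.

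Second, 6.25.1 defines transplant qualification as a clinical outcome, whereas Table 6 defines an event for a 24-week histological estimand. A stricter failure rule can be a deliberate choice, so the mismatch alone does not prove Table 6 wrong. But nothing visible gives a reason for counting an anticoagulant effect as treatment failure, and criterion 3f deliberately admits the subjects concerned.

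Third, a reader might infer that every eligible anticoagulated subject becomes a non-responder. The documents do not support that. At INR 1.5 the assumed formula gives 11.0, and at 2.0 it gives 14.2. Only a subject who reaches 15 is affected, and only if the biopsy would otherwise have counted as a response. The documents say neither how many subjects are anticoagulated nor to what INR.

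Fourth, a reader might infer that one or two such subjects could overturn the primary result. With an assumed 36 biopsies per arm and a Pearson test, 15/36 against 7/36 gives p = 0.041, and removing one EFX responder (14/36 against 7/36) gives p = 0.070. That case is chosen to sit at the boundary and removes a responder from one arm only. Removing one from each arm (14/36 against 6/36) gives p = 0.035. Starting from 17/36 against 5/36 (p = 0.002), losing one EFX responder gives 0.004 and losing two gives 0.009. Completer numbers are redacted, so the documents give no ground for predicting a reversal.

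**Conclusion.** The point holds as a rule that misfires when followed literally. Table 6 can score a subject with a responding Week 24 biopsy as a non-responder because an anticoagulant raised the INR, on the primary and the secondary histological endpoints alike. Section 6.25.1 exempts exactly this cause at the same threshold.

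The likely size is small. Randomization should make reclassification roughly equal across arms, so the expected result is dilution of the difference rather than a bias toward EFX. If 2.5% of each arm were affected, the cost is 0.7 to 1.7 points of power with EFX at 46.2%. The actual share is unknown and may be zero.

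This rests on the conventional MELD formula, on assumed placebo rates, and on Protocol Table 6 being the rule in force. Confidence is moderate, mainly because SAP Table 1 cannot be read. The change is worth making because the rule contradicts its own purpose and costs little to correct.

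**What to change.** Reconcile Protocol 7.5 (Table 6) with 6.25.1, and amend SAP Table 1 if it has the same wording:

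- Exclude from the intercurrent event a MELD of 15 or more that is due to therapeutic anticoagulation, including one already present at baseline. SAP 7.4 already summarises baseline MELD, so these subjects can be identified.
- State whether a repeat value is needed. Copying the 6.25.1 interval unchanged does not work cleanly: a value first seen after Week 20 cannot be confirmed at least 4 weeks later by Week 24, while the biopsy window runs from 2 weeks before to 4 weeks after that visit. If a repeat is required, say how an event too late to be confirmed is classified.
- State the MELD formula and whether the score is rounded, because rounding moves the threshold INR from 2.15 to 2.06.

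Settle this before unblinding. The cost is a few lines of text. INR, bilirubin, creatinine and concomitant medication are already collected, so no new data are needed.
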